8.5.5.3 Sleep Attacks

In order to prospectively monitor for the possible development of sleep attacks the following questions will be asked of subjects at each visit:

Since your last visit (or time this question was asked), have you experienced any events in which you fell asleep suddenly or unexpectedly, including while engaged in some activity (e.g., eating/drinking, speaking, or driving) or at rest, with or without any previous warning of sleepiness?

- If yes, what specifically happened?
- How many times did you experience such events?
- What were you doing at the time of each event?
- Prior to each event did you experience any sleepiness or drowsiness? If yes, please explain/clarify.
- How long did each event last?

- Did you suffer any "bad" outcome/problem from each falling asleep event?

The summary of sleep attacks will include the incidence of subjects with sleep attacks and the incidence of subjects with "bad outcomes" at Baseline and at any time during the Treatment Period. Summaries of sleep attacks by visit will be considered if the initial results indicate a high incidence of subjects with sleep attacks.

8.5.5.4 Minnesota Impulsive Disorders Interview (MIDI)

In order to monitor for the development of intense impulsive behavior the Minnesota Impulsive Disorder Interview (MIDI) will be administered at each visit. The MIDI is a semi-structured clinical interview assessing pathological gambling, trichotillomania, kleptomania, pyromania, intermittent explosive disorder, compulsive buying, and compulsive sexual behavior. A subject's MIDI screen is positive for a disorder if:

- Buying Disorder: Positive screen if the subject answers "yes" to 1a, 2a, 3a, and 4a
- Kleptomania: Positive screen if the subject answers "yes" to 1a, 2a, 3a, and 4a
- Trichotillomania: Positive screen if the subject answers "yes" to 1, 3, 4a, 5, and 6
- Intermittent Explosive Disorder: Positive screen if the subject answers "yes" to 1a, 1b, 1c, and 1d; in addition, the subject must answer "no" to 1f
- Pyromania: Positive screen if the subject answers "yes" to 1a, 2, 3, 4, and 5; in addition, the subject must answer "no" to 1b, 1c, 1d, and 1e
- Pathological Gambling: Positive screen if the subject answers "yes" to 1, and to at least 5 of the rest of the questions
- Compulsive Sexual Behavior: Positive screen if the subject answers "yes" to 1, 2a, 3a, or 4a

The incidence of subjects who report intense impulsive behavior at Baseline and at any time during the Treatment Period will be provided. Summaries of MIDI assessments by

visit will be considered if the initial results indicate a high incidence of subjects with intense impulsive behavior.

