6.4.5 Baseline Period for Study 3005

The Baseline Period for Study 3005 is defined as the time before the first 3005 LCIG infusion. For efficacy measures, the final value in the previous study (Study 3003 or Study 3004) will be retrieved from the relevant database and will be considered the 3005 baseline value. For safety evaluations, the final assessment in the previous open-label LCIG study or in 3005 that is on or before the date of the first 3005 LCIG infusion will be used as the 3005 Baseline value. For systolic blood pressure, diastolic blood pressure and

pulse, the final assessment where results are present for both the supine and standing position will be considered baseline.

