7.2 Secondary Objectives

To assess the long-term safety and tolerability of the LCIG therapeutic system by the following:

- Physical examination, including weight
- Neurological examination
- Vital signs
- Resting ECGs
- Clinical laboratory assessments including biochemistry, hematology, urinalysis, and special labs to monitor for vitamin deficiencies
- Concomitant medication usage
- Adverse event monitoring, including for the development of sleep attacks, melanoma, or excessive impulsive behavior
- Monitoring complications of the infusion device
- Tolerability assessed by number of subjects who complete the study

To assess the maintenance of efficacy using the following data collected from US subjects:

- Off time, On time with troublesome dyskinesia, and On time without troublesome dyskinesia as measured by the Parkinson's Disease Diary
- UPDRS total score, Parts I, II, III and IV scores, and dyskinesia item score
- PDQ-39 summary index and domain scores

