- DCT006 Overview of Device Complications (same categories as DCT005) for each 3005 Treatment Year (as defined in Section 6.4.9).
- DIT001 A summary of PEG tube replacements will be presented, for all centers/countries combined, using default summary statistics. A similar summary will be presented for J tube replacements.
- DIT002 A summary of PEG tube and J tube replacements will be presented for each 3005 Treatment Year (as defined in Section 6.4.9).
- DIT003 The average PEG tube and J tube duration in Study 3005 will be summarized with default summary statistics and with the number and percentage of subjects with average durations in 3 month time intervals (≤ 91 days, 92 – 182 days, 183 to 273 days, 274 to 365 days, or > 365 days).
- QST001 A summary of sleep attacks will be presented, for all centers/countries combined, using default summary statistics.

- QST002 A summary of the development of intense impulsive behavior as assessed by the Minnesota Impulsive Disorders Interview (MIDI) will be presented, for all centers/countries combined, using default summary statistics.
- QST003 A summary of suicidal ideation and behavior as assessed by the Columbia Suicide Severity Rating Scale (C-SSRS) will be presented, for all centers/countries combined, using default summary statistics.

In addition, the other safety analysis data will be presented as follows:

- DCL001 A listing of device complications with the standard demographic data will be presented by-subject.
- DIL001 A listing of device information with the standard demographic data will be presented by-subject.
- PEL001 A listing of results of melanoma checks with the standard demographic data will be presented by-subject and within-subject by visit.
- QSL008 A listing of sleep attack responses with the standard demographic data will be presented by-subject and within-subject by visit.
- QSL009 A listing of MIDI responses and positive/negative assessment for impulsive behavior with the standard demographic data will be presented by-subject and within-subject by visit.
- QSL010 A listing of C-SSRS responses with the standard demographic data will be presented by-subject and within-subject by visit.

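### The planned sleep-attack and MIDI summary tables do not isolate new onset during Study 3005

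*SAP*

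**What the plan says.** SAP 7.2 lists among the secondary safety objectives: "Adverse event monitoring, including for the development of sleep attacks, melanoma, or excessive impulsive behavior". SAP 9.11.5 describes the MIDI table (QST002, number 14.3__7.2) in the same terms: "A summary of the development of intense impulsive behavior as assessed by the Minnesota Impulsive Disorders Interview (MIDI) will be presented".

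The derivations are in SAP 8.5.5.3 and 8.5.5.4. For the MIDI: "The incidence of subjects who report intense impulsive behavior at Baseline and at any time during the Treatment Period will be provided". For sleep attacks (table 14.3__7.1): "The summary of sleep attacks will include the incidence of subjects with sleep attacks", and likewise for bad outcomes, "at Baseline and at any time during the Treatment Period. Summaries of sleep attacks by visit will be considered". By-visit tables are conditional for both measures. For sleep attacks: "Summaries of sleep attacks by visit will be considered if the initial results indicate a high incidence of subjects with sleep attacks". The MIDI wording is parallel: "visit will be considered if the initial results indicate a high incidence of subjects with intense impulsive behavior". Neither section says what counts as high.

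Baseline is a single look under SAP 6.4.5: "For safety evaluations, the final assessment in the previous open-label LCIG study or in 3005 that is on or before the date of" (quoted in part; Day 1 is meant). Later looks are 6-monthly plus termination (Protocol 11.1.4 and Table 2), and SAP Table 2 has windows out to Month 84. The sleep-attack question asks about the time since the previous visit, so Baseline covers one recall interval and treatment covers many.

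**The concern.** Development means that a subject who did not show the behaviour at entry shows it later. The committed tables give two separate percentages and no cross-classification. They have no baseline-negative denominator, no shift table and no adjustment for length of follow-up. Two things are therefore mixed in the any-time column: new cases with persisting ones, and risk with the number of times a subject was asked.

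The SAP handles this elsewhere. Potentially clinically significant laboratory and vital-sign values must be more extreme than Baseline (8.5.2, 8.5.3). Treatment-emergent adverse events (TEAEs) must start on or after the first 3005 infusion (8.5.1). Adverse events and device complications are also tabulated by 3005 Treatment Year with follow-up-based denominators. Sleep attacks and MIDI are not among the events assigned to Treatment Years in 6.4.9.

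At stake is whether the summary tables for these two measures can answer the question they are described as answering.

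**Working it through.** The documents state no event rate, power or alpha for these summaries (Protocol 13.4: not applicable), so there is no planned figure to reproduce. The rates, counts and correlations below are assumptions for illustration.

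**Inputs from the documents.** N is about 275 (Protocol 7.1). There is one baseline look (SAP 6.4.5). Post-baseline looks come every 6 months: 84/6 = 14 windows to Month 84 (SAP Table 2), and 4 × 2 = 8 for a subject followed through the expected 4 years (Protocol 7.1).

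**1. What the two margins reveal about new onset.** Let B be the number positive at Baseline and T the number positive at any time, with all N subjects assessed at both. At most B of the T cases were already positive, so the new-onset count lies between max(0, T − B) and min(T, N − B).

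- B = 14, T = 14: 0 to 14 new cases, or 0 to 14/261 = 5.4% of baseline-negatives.
- B = 14, T = 30: 16 to 30, or 6.1% to 11.5%.
- B = 3, T = 10: 7 to 10, or 7/272 = 2.6% to 10/272 = 3.7%.

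The bound is wide when B is close to T and tight when B is small.

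**2. Effect of unequal looks with no change in risk.** Let p be the constant probability of a positive result per visit.

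- Independent visits: P(any of k) = 1 − (1 − p)^k.
- Within-subject correlation ρ between 0 and 1 (beta-binomial), with a = p(1 − ρ)/ρ and b = (1 − p)(1 − ρ)/ρ: P(any of k) = 1 − Γ(b + k)Γ(a + b) / [Γ(b)Γ(a + b + k)].
- ρ = 1: P(any of k) = p.

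For p = 2%:

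| ρ | 8 visits | 14 visits |
|---|---|---|
| 0 | 14.9% | 24.6% |
| 0.3 | 7.5% | 9.6% |
| 0.6 | 4.5% | 5.2% |
| 0.9 | 2.5% | 2.7% |
| 1 | 2.0% | 2.0% |

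Over 14 visits, p = 1% gives 13.1% at ρ = 0 and 2.6% at ρ = 0.6; p = 5% gives 51.2% and 12.5%. At any ρ below 1 the any-time figure exceeds the Baseline figure although the risk is constant.

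**3. How much of the any-time column is new onset.** The probability of being negative at Baseline and positive at any of k later visits is P(any of k + 1) − p. With p = 2%, k = 8, N = 275 and B = 5.5 expected:

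- ρ = 0: T = 41.0, new onset 40.2 (14.9% of baseline-negatives).
- ρ = 0.6: T = 12.3, new onset 7.2 (2.7%); the other 5.1 were already positive.
- ρ = 1: T = 5.5, new onset 0.

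The first line shows that a baseline-negative denominator alone does not correct for repeated looks: it returns the same 14.9% as the any-time column. The two problems need separate remedies.

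**The case against.** A reader might infer that new onset cannot be seen at all. The documents do not support that. Listings QSL008 and QSL009 give sleep-attack and MIDI results by subject and visit, so new cases can be counted by hand. T − B is a lower bound. The objective itself names adverse event monitoring, and TEAEs are new-onset by definition and tabulated by Treatment Year. That route is incomplete, however. SAP 8.5.5.3 and 8.5.5.4 do not require a positive answer to be recorded as an adverse event, whereas neurological abnormalities (8.5.5.7) and clinically significant laboratory and ECG findings (8.5.2, 8.5.4) must be. Neither behaviour is an adverse event of special interest in 8.5.1.

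A reader might also infer a rule that counts baseline-positive subjects again, or a formal judgement based on the two columns. The SAP is silent on the first: with no exclusion stated, such subjects would be counted if positive again, but that is inference. On the second, the tables are descriptive and follow Protocol 13.3, with no test or decision rule.

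Baseline positives may be few. Protocol 8.2 excludes clinically significant psychiatric issues that could interfere with participation, and Protocol 11.1.4 provides for discontinuation for clinically significant impulsivity. This would tighten the bound for MIDI. It does not cover positive screens judged not clinically significant, and no equivalent discontinuation provision is given for sleep attacks.

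Independence between visits is the upper case, and 14 is the last window rather than the expected number of visits. An any-time figure raised by repeated looks would also make the conditional by-visit tables more likely, not less. These points reduce the size of the problem. None of them makes the tables show new onset.

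**Conclusion.** The concern holds in a limited form. Tables 14.3__7.1 and 14.3__7.2 as specified cannot separate new onset from persistence, and they set a single look beside an accumulating one. The only planned refinement depends on an undefined threshold.

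The size depends on rates and correlations that the documents do not give. For an assumed 2% per visit, the apparent any-time figure with no change in risk runs from 2.0% to 24.6% over 14 visits, and from 2.0% to 14.9% over 8. The lower part of each range applies if status is strongly persistent.

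One further reading is tempting: that a corrected table would show emergence on LCIG. It would not. Subjects enter Study 3005 already on open-label LCIG, so the quantity obtainable is onset during 3005. Because the tables are descriptive, secondary and backed by listings, this is a modest and inexpensive improvement that would let them answer their stated purpose.

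**What to change.** In SAP 8.5.5.3 and 8.5.5.4, with matching blocks in tables 14.3__7.1 and 14.3__7.2:

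1. Add a shift table of Baseline status by any post-baseline positive. Report new onset with baseline-negative subjects as the denominator, show baseline-positive subjects separately as persistent or resolved, and give subjects with no Baseline answer their own row.
2. Because step 1 does not correct for unequal follow-up, either make the by-visit percentage of subjects assessed a fixed table, so that one look is compared with one look, or report new onset by 3005 Treatment Year using the follow-up-based denominator that 8.5.1 already applies to adverse events. The undefined 'high incidence' condition can then be dropped.

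The cost is SAP wording, two added table blocks and the missing-Baseline row. No new data are needed, since the inputs are already listed by subject and visit.

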8.5.5.5 Columbia Suicide Severity Rating Scale (C-SSRS)

The Columbia-Suicide Severity Rating Scale (C-SSRS)⁵ is a systematically administered instrument developed to track suicidal adverse events across a treatment study. It was added to the flowchart of study assessments (Appendix 12.1.3) with Protocol Amendment 3. At each study visit, the C-SSRS will collect experience since the last visit. The incidence of subjects with affirmative responses on the C-SSRS at any time during the Treatment Period will be provided.

Each summary will include the number and percentage of subjects with one or more affirmative responses to each of the 5 suicidal ideation questions, each of the 6 suicidal behavior questions, any of the 5 suicidal ideation questions, any of the 6 suicidal behavior questions, any suicidal ideation or behavior question, and the non-suicidal self-injurious behavior question.

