11.1.5 Columbia-Suicide Severity Rating Scale (C-SSRS)

The Columbia-Suicide Severity Rating Scale (C-SSRS)¹⁶ is a systematically administered instrument developed to track suicidal adverse events across a treatment study. The instrument is designed to assess suicidal behavior and ideation, track and assess all suicidal events, as well as the lethality of attempts. Additional features assessed include frequency, duration, controllability, reason for ideation, and deterrents. The C-SSRS is considered a low-burden instrument, as it takes less than 5 minutes to administer. Raters will receive instruction on the administration of the C-SSRS assessment scales prior to administration of the scales. The C-SSRS will be administered at the times outlined in [Table 2](#).

Subjects expressing suicidal ideation with plan, either by answering "yes" to questions 4 and/or 5 to the suicidal ideation portion of the C-SSRS or via clinical interview, will be evaluated immediately by the Investigator or another medically qualified individual (M.D., D.O.). The Medical Monitor must be notified and the subject will be discontinued from participation in the study. The subject will be referred for appropriate psychiatric follow-up treatment, if necessary, per the judgment of the Investigator or the medically qualified individual. The Medical Monitor will also be notified. In addition, if the subject expresses suicidal ideation or suicidal behavior at any time during the course of the study, the subject should be discontinued from participation in the study and referred for proper psychiatric follow-up care. The Investigator and the Medical Monitor should be notified immediately as well.

Under no circumstances should a subject who has positively endorsed or expressed suicidal ideation or behavior be left alone, be allowed to exit the site, or go home before a qualified medical professional has evaluated the subject's risk.

The "Already Enrolled Subjects" C-SSRS will be the first assessment scale administered to the subject. At each subsequent assessment, the "Since Last Visit" C-SSRS scale should be administered.

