11.6 Flow Chart of Study Assessments

All study assessments will be conducted as indicated in [Table 2](#), which displays the frequency and timing of all measurements. Subject visit days should ideally match the target clinic visit days; however, a ± 14 day visit window will be allowed as necessary for the 6 Monthly visits and a ± 7 day visit window will be allowed for clinical supply visits. Every attempt should be made to bring the subject back on the target visit day.

Table 2. Flow Chart of Study Assessments

Visit	Baseline	6 Monthly Visit	Termination/ Transfer to Commercial	Follow-up*
Day	Final Assessment in Previous Study	+/- 14 Days	--	Termination Visit + 7 Days
Informed consent	X			
Inclusion/exclusion	X			
Physical exam	X ^a	X	X	
Neurological Exam	X ^a	X	X	
Weight	X ^a	X	X	
Vital signs	X ^a	X	X	X
12-lead ECG	X ^a	X ^b	X	
Clinical labs	X ^a	X ^b	X	
Folic Acid, Vitamins B6, B12, Methylmalonic Acid (MMA), and Homocysteine Levels	X ^a	X	X	
β-HCG ^c	X ^a	X	X	
Adverse events**	X ^a -----X			
Concomitant medication	X ^a	X	X	X
Sleep attacks	X ^a	X	X	
Melanoma check	X ^a	X ^d	X	
Determination of continued benefit***	X	X		
MIDI	X ^a	X	X	
C-SSRS ^f	X ^a	X	X	X
Complications with infusion device	X ^a	X	X	
Inspection of stoma	X ^a	X	X	X
Assessment of the need to replace PEG-J****	X	X ^d		
Dispensing of study drug	X-----Every 6 weeks ^e -----			
Daily Dosing Diary ^g		X	X	

Table 2. Flow Chart of Study Assessments (Continued)

Visit	Baseline	6 Monthly Visit	Termination/ Transfer to Commercial	Follow-up*
Parkinson's Disease Diary ^g		X	X	
UPDRS ^h		X	X	
PDQ-39 ^h		X	X	
Removal of PEG*****			X	

- * This visit needs to be performed only if PEG-J is removed, or if the subject does not continue to receive drug after termination.
- ** Collection of adverse events is an ongoing and continuous process, not only occurring during site visits.
- *** The decision to continue subjects on LCIG treatment will be dependent upon Principal Investigator's clinical judgment.
- **** On a yearly basis, the LCIG system check needs to be evaluated by the study gastroenterologist; frequency of replacement should be in accordance with local practice.
- ***** For subjects deemed inappropriate for continued treatment by the Investigator, or for subjects who elect not to continue LCIG treatment, the PEG-J will be removed, and a follow-up clinic visit will occur 1 week later.

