6.4.6 Treatment Period

Data collected on the Date of the First 3005 LCIG Infusion (Day 1) will be assigned to the Baseline Period. However, adverse events and concomitant medications starting on Day 1 will be assigned to the Treatment Period (worst case scenario).

A Gap Period (number of days) is defined to include data collected after the end of the relevant Treatment Period in the analysis. For this study, the Gap Period will be 30 days for adverse events and 1 day for all other assessments.

For efficacy assessments the Treatment Period is defined as the Period from the Date of the First 3005 LCIG Infusion up to and including the Date of the Last 3005 LCIG Infusion + Gap Period (1 day). For safety assessments the Treatment Period is defined as the Period from the Date of the First 3005 LCIG Infusion up to and including the Date of the Last 3005 PEG-J Exposure + Gap Period (30 days for adverse events and 1 day for all other assessments).

The Endpoint value for a variable is defined as the last non-missing value assigned to the Treatment Period for the subject.

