6.4.7 Post-Treatment Period

For efficacy assessments, the Post-Treatment Period is defined as the period after the Date of the Last 3005 LCIG Infusion + Gap Period (1 day). For safety assessments, the Post-Treatment Period is defined as the period after the Date of the Last 3005 PEG-J Exposure + Gap Period (30 days for adverse events and 1 day for all other assessments).

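### The scheduled Follow-up C-SSRS normally falls outside the SAP's Treatment Period, so it is listed but left out of the only C-SSRS summary table

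*SAP*

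**What the plan says.** **Collection.** Protocol 11.1.5 ties the schedule to the flow chart ("The C-SSRS will be administered at the times outlined in" Table 2). The C-SSRS row of that table is marked at Baseline, the 6-monthly visits, Termination and Follow-up. Follow-up is timed as "Termination Visit + 7 Days". For subjects who stop LCIG, a footnote says that "the PEG-J will be removed, and a follow-up clinic visit will occur 1 week later". The SAP reproduces this schedule in Appendix 12.1.4.

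**Summary.** SAP 8.5.5.5 states: "The incidence of subjects with affirmative responses on the C-SSRS at any time during the Treatment Period will be provided". The resulting table is 14.3__7.3 (SAP 9.11.5 and 12.2). No other C-SSRS table is planned. Listing QSL010 shows all responses by subject and visit.

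**Window.** SAP 6.4.6 says "the Gap Period will be 30 days for adverse events and 1 day for all other assessments". For safety assessments the Treatment Period runs "up to and including the Date of the Last 3005 PEG-J Exposure + Gap Period". SAP 6.4.7 assigns the remainder: "For safety assessments, the Post-Treatment Period is defined as the period after the Date of the Last 3005 PEG-J Exposure + Gap Period". Follow-up is a visit label in SAP Table 1 but has no row in the visit windows of SAP Table 2.

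**Adverse events.** SAP 8.5.1 counts an event as treatment-emergent if it starts within 30 days of last PEG-J exposure.

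**The concern.** The protocol asks every subject who stops LCIG, and whose visit falls under the Amendment 3 or 4 schedule, to answer the C-SSRS once more a week after PEG-J removal. According to SAP 8.5.5.5 the form covers the time since the previous visit, so the Follow-up form describes the first week off treatment. The one-day gap sends that form to the Post-Treatment Period, for which no C-SSRS summary is planned.

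This looks more like the side effect of a general rule than a decision about suicidality. SAP 8.5.5.3 and 8.5.5.4 restrict the sleep-attack and MIDI summaries to the same period, but neither of those is scheduled at Follow-up, so nothing is lost. The C-SSRS is scheduled there. Protocol 13.3 asks for a summary of the C-SSRS without limiting the period, and SAP 10.1 does not mention the restriction.

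What is at stake is a positive answer given for the first time, or to a new item, at Follow-up. If the site does not also record it as an adverse event, it would appear only in a listing. If the site does record it, the adverse event tables count the subject and the C-SSRS table may not.

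**Working it through.** The plan gives no figure to reproduce, and no power or alpha calculation applies. The check is day arithmetic on the SAP's own rule.

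**Inputs**
- Termination visit = day 0 and Follow-up visit F = day 7 (Protocol Table 2).
- R = date of last PEG-J exposure (SAP 6.4.1). This is the PEG-J removal date if the removal is recorded after the last dose. Otherwise it is the date of discontinuation or completion on the disposition page. At the interim analysis it is also limited by the Cutoff Date.
- g = gap: 1 day for the C-SSRS, 30 days for adverse events (SAP 6.4.6).

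**Rule:** the Follow-up C-SSRS enters Table 14.3__7.3 only if F ≤ R + g.

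**With the planned gap (g = 1) and the visit at day 7**

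| Last PEG-J exposure R | Window closes at R + 1 | Follow-up at day 7 |
|---|---|---|
| day 0 (removal or disposition date at Termination) | day 1 | out, by 7 − 1 = 6 days |
| day 3 | day 4 | out, by 3 days |
| day 5 | day 6 | out, by 1 day |
| day 6 | day 7 | in |
| day 7 (no qualifying removal; disposition date = Follow-up date) | day 8 | in |

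**With the visit timed from removal (F = R + 7).** The condition becomes R + 7 ≤ R + g, that is g ≥ 7. A gap of 1 or 6 days excludes an on-time visit; 7, 14 or 30 days includes it.

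**Adverse events on the same pathway.** With R = 0 the window closes on day 30, so an event starting on days 1 to 7 is treatment-emergent.

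**Do the adverse event tables cover the gap?** SAP 8.5.2, 8.5.4 and 8.5.5.7 state that clinically significant laboratory results, clinically significant ECG abnormalities and neurological abnormalities are to be reported as adverse events. Protocol 11.1.5 and SAP 8.5.5.5 contain no matching sentence for a positive C-SSRS answer. Protocol 12.1.1 says that an adverse event may be inferred from study-specified tests; that permits such an entry but does not require it. Part of Protocol 12.2.1, on reporting serious events, was not available for this review.

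**The case against.** **The window is a stated, uniform rule.** One day applies to all safety data other than adverse events, and vital signs taken at Follow-up are treated in the same way. An on-treatment table is a legitimate choice, and tables with different windows may differ without either being wrong. This stands. It is a reason to leave the Treatment Period incidence as it is, but not a reason to tabulate the Follow-up answers nowhere.

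**Suicidal events in that week are not lost.** A reader might infer that they are never summarised, or that Table 14.3__7.3 is the only summary of suicidality. The documents do not support either reading. Events recorded as adverse events within 30 days enter the treatment-emergent tables, and again the serious, fatal or termination tables where they qualify. All C-SSRS answers are in QSL010. Table 14.3__7.3 is only the sole C-SSRS summary.

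**Exclusion is not universal.** The window is anchored on PEG-J exposure, not on the last infusion. Removal on day 6 or later, with the visit kept at Termination + 7, brings the visit inside. So does a disposition date on the Follow-up day when no qualifying removal is recorded. Subjects who continue on commercial product need no Follow-up visit.

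**Subjects stopped because of ideation are normally already counted.** It is tempting to say that the table misses exactly these subjects. However, a C-SSRS is scheduled at Termination and covers the time since the previous visit, so the answer that led to stopping normally falls inside the Treatment Period. The table counts a subject with any affirmative response in that period. Only a first or newly positive answer at Follow-up is exposed.

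**Conclusion.** The point holds in a limited form. When the PEG-J is removed at Termination and Follow-up takes place 7 days later, the Follow-up C-SSRS is 6 days past the window. It is listed but not tabulated. Because no stated rule in the reviewed text turns a positive answer into an adverse event, a first or newly positive answer at that visit could appear in no table.

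The number of assessments affected cannot be derived from the documents. A reader might multiply the planned 275 subjects by an assumed discontinuation rate, but that would count subjects who stop, not excluded assessments. The C-SSRS was added only with Amendment 3, so subjects who stopped under earlier schedules have no Follow-up form. Some who stop will not attend, and the exceptions above remove others.

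The conclusion assumes that visits take place as scheduled and that the SAP's date rules are programmed as written. The study is single-arm and descriptive, so no test or estimate of treatment effect is affected. What is affected is the completeness of one safety table.

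**What to change.** In SAP 8.5.5.5, keep the Treatment Period incidence unchanged and add a separate Follow-up/Post-Treatment row or column to Table 14.3__7.3. Use the same response categories, with the number of subjects who have a Follow-up C-SSRS as denominator. Assign assessments by SAP 6.4.6 and 6.4.7, so that a Follow-up visit that falls inside the window stays in the Treatment Period count and is not counted twice.

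Applying the 30-day adverse event gap to the C-SSRS would also capture the visit, but it is the weaker choice because it mixes off-treatment answers into an on-treatment rate.

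The cost is one sentence in the SAP and one extra row or column. No new data are needed. The drawback is that the new entry may rest on a small denominator, which the table should show.
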